4. SCHEDULE OF EVENTS

This study requires a minimum of nine study visits to the MARC, CTRC, and/or UHS. The research staff will try to schedule these study visits at the same time as the patient's routine follow-up visits as much as possible to lessen the participant's burden. Since this study is a comparison of two standard of care treatments, participant will not be limited to receiving treatments (i.e. radical cystectomy, radiation, and/or chemotherapy) at UTHSCSA affiliated medical facilities. If participant choose to receive treatment (i.e. radical cystectomy, radiation, and/or chemotherapy) outside of UTHSCA affiliated medical facilities and still would like to remain in the study, we will request for the participant to release his/her medical records and treatment summaries from outside facilities to us after treatment completion. Participant will return to MARC, CTRC, and/or UHS for the routine post-treatment follow-up visits with the treating Urologist. The specific location for the follow-up routine visits will be to the discretion of the treating physician and also the participant's insurance coverage. A summary of study schedule of events is as follows:

4.1 Screening and enrollment

Research staff will review clinic schedules to identify potential participants. Treating Physicians/Physician's Assistant/Nurse Practitioner seeing patients at the MARC Urology Clinics, CTRC will also identify study candidates. Advertising material such as a study flyer will also be placed in the Urology clinics to facilitate with participant recruitment. Potential study candidates identified by the research staff and the information regarding study eligibility will be made available to the treating physician who provides clinical care and sees the patient in clinic. The treating physician, physician assistants (PA), or nurse practitioner (NP) will make initial contact with patients whose pre-screening/chart review indicates they may be eligible for study participation.

Interested participants may also contact the research staff, and if determined possibly eligible for study participation, are scheduled for a research appointment. Screening information collected on ineligible participants will be shredded at the end of study recruitment.

Once the patient has been determined to meet pre-screening criteria, potential participants will first be approached in their private examination room by their treating medical provider, who may also be a research investigator. If the patient indicates an interest in study participation, he will be provided further information about the study, answer questions, and provide a copy of the consent form. The individual will be encouraged to take the consent form home to read and discuss with family, friends, or physicians. If interested, the potential participant will be scheduled to come in and sign consent and undergo study assessments.

The technical aspects of the study will be discussed with potential participants by the Principal Investigator, approved research team members and/or by study co-investigators. Research staff members who are IRB approved and designated for that role will conduct the consent process. The following consent elements will be discussed: voluntary nature of participation, purpose of the study, study procedures, risks and benefits, the collection of protected health information, confidentiality, and participant rights. The participant will be given a copy of the informed consent

to read and consider and ample opportunity will be given to answer any questions. The participant may decline to participate, decide to participate, or take the consent home to think about participating. A copy of the signed consent form will be provided to each participant.

The potential participant will then be scheduled for a TURBT (transurethral resection of bladder tumor) with the treating urologist, which may also be the study's principal investigator or co-investigator. TURBT is the standard of care which allows the treating urologist to formally assess the extent of disease progression and also to evaluate whether the candidate can be treated with both radical cystectomy and chemoradiation treatment. Potential participant will be approached to store any leftover tissue specimens, not needed for diagnosis, into the "GU Tissue Bank" (IRB HSC20050234H). The tissue collected will be processed per standard of care, and slides or tissue blocks may be accessed later for future use in correlative studies. The leftover specimens may be used for future research studies that may include genetic testing related to bladder cancer. This banking portion is optional and not required to be in the main study. If the participant declines to participate in the optional study, any leftover specimens will be permanently de-identified through the GUTB (05-234H).

The potential participant will then return to the clinic for a routine follow-up visit to review the TURBT results and discuss treatment options with the treating Urologist within 4 weeks post-TURBT. Final eligibility will be determined during the TURBT follow-up visit. If potential participant is eligible for the study, randomization will occur. The following section outlines study procedure during the visit.

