Given the potential non-inferiority of chemoradiation relative to radical cystectomy, clinical prediction of non-response to chemoradiation in terms of biomarkers would be of interest. However, there is paucity of predictive markers that can identify non-responders of chemoradiation. If predictive markers could be identified, patients might then be selected for the treatment most likely to benefit them, which would have the added advantage of maximizing overall cure rates and minimizing poor outcomes. Characterization of the genomic drivers of bladder cancer has been proposed for evaluating progression. Immunohistochemistry has been utilized with limited accuracy. A number of investigators have queried whether comprehensive genomic profiling of cancer-related genes could potentially assist in the selection of targeted therapies for patients with radiation refractory bladder cancer.³ As part of our pilot study, we propose to perform microarray gene expression profiling using Agilent long oligonucleotide (60 mers) technology to search for molecular alterations differing between responders and non-responders of chemoradiation with radical cystectomy as a reference.

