2. HYPOTHESIS AND SPECIFIC AIMS

Multiple prospective radiation therapy protocols have evaluated bladder-preserving chemoradiation therapy approach for muscle-invasive bladder cancer (MIBC), with radical cystectomy reserved for radiation failure. Aims of bladder preservation in MIBC are to offer a quality-of-life advantage and avoid potential morbidity or mortality of RC without compromising oncologic outcomes. Because of lack of level-1 evidence, oncologic equivalence of bladder preservation modality treatments compared with RC remains unknown.

2.1 HYPOTHESIS:

We hypothesized that chemoradiation is non-inferior to radical cystectomy for treatment of MIBC.

2.2 SPECIFIC AIMS:

SPECIFIC AIM 1a To determine and quantify quality of life in patients treated with radical cystectomy and chemo radiation therapy

1b To determine and quantify progression free survival and bladder-intact survival in patients treated with radical cystectomy and chemoradiation therapy,

SPECIFIC AIM 2a To evaluate genetic markers predicting response to chemoradiation by performing tissue RNA microarrays.

2b To assess the feasibility of conducting an adequately powered non-inferiority trial of the same design via recruitment rate, patient adherence to both treatment arm, and attrition.

2.3 STUDY DESIGN:

Our study will be a pilot, prospective, single-center, randomized non-inferiority trial comparing chemoradiation therapy to radical cystectomy. Patients diagnosed with muscle invasive bladder cancer after transurethral resection of bladder tumor and are surgical candidates will be randomized to either radical cystectomy (with neoadjuvant chemotherapy if suitable candidate) or chemoradiation.

Both treatment methods are considered “standard of care” recommended by the NCCN Clinical Practice Guidelines (http://www.nccn.org/professionals/physician_gls/pdf/bladder.pdf) in treating muscle invasive bladder cancer.

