4.3. Required Evaluations/Management (baseline prior to initiation of any protocol treatment)

- a) Cystoscopic evaluation by the participating urologic surgeon no more than 6 weeks prior to registration will include bimanual examination under anesthesia, as thorough as possible, a transurethral resection of the bladder tumor. Patients referred from an outside hospital with a muscularis propria-invading bladder tumor will be re-resected by the participating urologist.
- b) Radiologic evaluation including chest CT, abdominal and pelvic CT and bone scan no more than 6 weeks prior to start of treatment.
- c) Comprehensive metabolic panel (CMP) obtained no more than 4-6 weeks prior to registration

5. Randomization

5.1 Radical Cystectomy Arm- Those randomized to “Radical Cystectomy” will be scheduled for surgery. In brief, radical cystectomy is the removal of the entire bladder, nearby lymph nodes (lymphadenectomy), part of the urethra, and nearby organs that may contain cancer cells. In men the prostate, the seminal vesicles, and part of the vas deferens are also removed. In women the cervix, the uterus, the ovaries, the fallopian tubes, and part of the vagina are also removed. Participants in this group may also undergo neoadjuvant chemotherapy prior to the surgery as is the current standard of care. The decision for specific chemotherapy regimen is based on medical oncologist’s evaluation. All AE occurring during the study period will be assessed and attribution assigned.

The surgical approach, robotic versus open, is determined by patient and surgeon mutual preference. All urinary diversions will be done via an open incision and the mode of diversion, whether intracorporeal or extracorporeal (orthotopic neobladder, continent cutaneous diversion or ileal conduit) will be selected by mutual agreement of the surgeon and patient, as is customarily done. The extent of the lymph node dissection will be determined by the surgeon but at minimum will include the external iliac, obturator, and hypogastric regions.

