9. DATA COLLECTION & STUDY EVALUATIONS

Medical records will be reviewed prior to “Baseline Study Visit” to confirm study eligibility. After obtaining consent, socio-demographic data will be collected through chart review and interviews. Clinical data that will be collected include but not limited to bladder cancer treatment history, tumor characteristics, stage, laboratory results, medications and co-morbidity.

Study team member or clinic staff will measure height, weight, and vital signs at each specific study time point. Research blood will be drawn at each study time point. Blood and tissue samples may be banked under the optional study (HSC20050234H GU Tissue Bank). For those participants who declined to participate in the optional study, any leftover samples will be permanently de-identified through the GU Tissue Bank (HSC20050234H) honest broker system. At the close of this study, all biological materials collected will be rolled into HSC20050234 GU Tissue Bank.

9.1 Feasibility: We will report recruitment, visit dates, adherence, attrition rates and compliance with randomization for each arm of the study

9.2 Bladder-intact survival: We will report proportion of patients who failed chemoradiation and required salvage cystectomy

9.3 Quality of life: A self-assessment questionnaire using the European Organization for Research and Treatment of Cancer (EORTC) QLQ- C30 and FACT-Bladder will be used for QOL assessment at baseline, 3, 6, 9 and 12 months.⁸

9.4 Progression free survival: This will be measured from the date of finishing chemoradiation or radical cystectomy to the date of first documentation of progression. Progression will be determined using RECIST 1.1 criteria by the treating physician based on radiographic or pathologic evidence of disease progression, or death from disease. Any documented recurrence will be considered progression.⁹ The date of progression will be recorded.

9.5 Candidate gene expression analysis: For the participants who have consented to be part of the optional study (“GU Tissue Bank HSC20050234H), a microarray analysis will be performed on all bladder tumor specimens using Agilent Technologies (Agilent SurePrint G3 Human Gene Expression 8x60K v2) Microarray. Goal is to study the landscape of 50 important candidate genes, which are involved in bladder cancer (for example-BRAF, KRAS, EGFR, FGFR).

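### Aim 2a is an aim of this trial, but its assay is open only to members of a separate optional tissue bank, and the protocol text describes no consent to the assay apart from banking

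*Combined protocol and SAP*

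**What the plan says.** Section 2.2 lists Aim 2a among the trial's own specific aims: "To evaluate genetic markers predicting response to chemoradiation by performing tissue RNA microarrays". The Background describes the profiling as part of this pilot and gives its purpose, to "search for molecular alterations differing between responders and non-responders of chemoradiation with radical cystectomy as a reference".

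Section 9.5 restricts the assay. It is run "For the participants who have consented to be part of the optional study", meaning the GU Tissue Bank, which has its own IRB number. Section 4.1 presents that bank as a store of leftover tissue for future research and adds: "This banking portion is optional and not required to be in the main study".

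For those who decline, Section 4.1 states: "If the participant declines to participate in the optional study, any leftover specimens will be permanently de-identified through the GUTB (05-234H)". Section 9 applies the same rule to blood and tissue: "any leftover samples will be permanently de-identified through the GU Tissue Bank (HSC20050234H) honest broker system". Section 9 also states: "At the close of this study, all biological materials collected will be rolled into HSC20050234 GU Tissue Bank".

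The source tissue comes from a TURBT done before randomisation, and Section 4.3 adds: "Patients referred from an outside hospital with a muscularis propria-invading bladder tumor will be re-resected by the participating urologist". Section 6 records post-induction biopsy and cytology results for the chemoradiation arm. Section 11 does not say how participants without assayed tissue are treated in Aim 2a, and Section 9.1 does not list tissue availability among the feasibility measures.

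**The concern.** Two different permissions are tied together. One is for a defined assay that serves a stated aim of this trial. The other is for open-ended storage for unspecified later research. A patient may be willing to give the first and not the second, and the protocol text makes no provision for that patient. If the plan is followed as written, the patient's leftover tissue is not assayed, and once de-identified it cannot be matched to arm or induction response.

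This matters because the informative sample is very small. Response to chemoradiation exists only in the chemoradiation arm, planned at 15 patients, and non-responders are likely to be the scarcer group. Losing one or two of them changes what the analysis can show, and those left are a self-selected subset.

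**Working it through.** **Is there a planned figure to reproduce?** No. The documents give no sample size, power, effect size or banking rate for Aim 2a. The only sample-size calculation in Section 11 concerns quality of life and does not bear on this point.

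**Inputs from the documents**
- Chemoradiation arm: 15 of 30 (Section 3.3).
- Candidate genes: 50 (Section 9.5).

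**Assumptions (not in the documents)**
- Non-response after induction: 30%, range 20% to 40%. The Background says only that a majority respond and that more than 70% keep the bladder.
- Bank opt-in *u*: 70% as the main case, range 50% to 100%, independent of response.
- True difference between responders and non-responders in one marker: 1.5 SD.

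**1. Expected numbers with linkable tissue.** Patients = 15 × *u*; non-responders = 15 × *u* × 0.30.
- *u* = 1: 15 patients, 4.5 non-responders.
- *u* = 0.7: 10.5 patients, 3.15 non-responders.

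**2. Chance of losing at least one of the 15.** 1 − *u*^15. At *u* = 0.9 this is 1 − 0.206 = 79%. At *u* = 0.7 it is 99.5%.

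**3. Chance of two or fewer non-responders with linkable tissue.** Let X ~ Binomial(15, 0.30 × *u*) and compute P(X ≤ 2).
- *u* = 1, probability 0.30: 0.005 + 0.031 + 0.092 = 0.127.
- *u* = 0.7, probability 0.21: 0.029 + 0.116 + 0.216 = 0.361.

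| Non-response | *u* = 1 | *u* = 0.9 | *u* = 0.7 | *u* = 0.5 |
|---|---|---|---|---|
| 20% | 40% | 48% | 65% | 82% |
| 30% | 13% | 19% | 36% | 60% |
| 40% | 3% | 5% | 16% | 40% |

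**4. Power for one marker.** Two-sample t-test, two-sided 5%, noncentral t with df = n1 + n2 − 2 and noncentrality 1.5 × √(n1 n2 / (n1 + n2)). The responder to non-responder split is held at 70:30, so that only the number of patients changes. Fractional expected counts are used.

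| Tissue available from | n1 v n2 | df | Noncentrality | Power |
|---|---|---|---|---|
| All 15 | 10.5 v 4.5 | 13 | 2.66 | 69% |
| 70% opt-in | 7.35 v 3.15 | 8.5 | 2.23 | 51% |
| 70% opt-in, half the decliners accept the assay (85%) | 8.925 v 3.825 | 10.75 | 2.45 | 61% |

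The gross loss is 69 − 51 = 18 points. A separate assay line accepted by half the decliners recovers 61 − 51 = 10 of them.

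**5. Allowing for 50 genes.** At 0.05 / 50 = 0.001, power for the same 1.5 SD difference is 13% with all 15 patients and 5% at 70% opt-in.

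**The case against.** The strongest reply is that consent to genetic research on leftover tissue is properly voluntary, and that opt-in is not what limits Aim 2a. Both halves have force. The proposed assay line would also be optional, so self-selection would remain. With 50 genes and 15 patients the aim is weak even at full uptake (step 5). Section 11 also directs the Aim 2a analysis at differences between arms, which better consent would not change. What survives is narrower: voluntariness does not require tying the trial's own assay to open-ended banking, and a weak analysis has little room for avoidable loss.

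Some stronger readings are tempting, and the documents do not support them.
- *Patients have no way to accept the assay and refuse banking.* The consent form and the bank's own protocol are not among the documents reviewed, and either could offer tiered choices. Only the silence of the protocol text is established.
- *The trial already holds the tissue and response of every chemoradiation patient.* The rule covers leftover tissue not needed for diagnosis. Some patients may have none, and it is offered before arm or response is known.
- *The loss is certain and wholly irreversible.* The text does not say when de-identification happens, or that diagnostic material is included. The loss is zero if everyone opts in.
- *The whole drop in power is recoverable.* Only the part due to patients who refuse banking but accept the assay can be recovered.
- *Research blood should not be drawn from decliners.* The blood draw is a main-study procedure, and the documents do not tie its purpose to Aim 2a or the bank alone. No change is proposed there.

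**Conclusion.** The point holds as a gap in the protocol text. A main-trial aim depends on joining a separate optional bank, decliners' leftover samples are permanently de-identified, and no consent to the assay apart from banking is described. Any chemoradiation patient who declines banking but would have accepted the assay is an avoidable loss from at most 15.

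Its size cannot be known from the documents. The 13% to 36% and 69% to 51% figures rest on the assumed 30% non-response, 70% opt-in and 1.5 SD difference; the 61% figure also assumes that half the decliners accept the assay. The direction is the same across the ranges shown, but the amount varies widely. The change is worth making because it is cheap, although it will not turn Aim 2a into more than an exploratory analysis.

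**What to change.** 1. In Sections 4.1 and 9.5, place the Aim 2a assay of leftover TURBT tissue under main-study consent as its own optional line. Keep banking for future research as a second, separate optional line. If the consent form already offers this choice, bring the protocol text into line with it.
2. In Sections 4.1 and 9, for participants who accept the assay line but decline banking, de-identify leftover tissue only after the Aim 2a result has been linked to arm and response. This cannot apply to those who decline the assay.
3. In Sections 9.1 and 11, report by arm the number with linkable tissue out of the number randomised, and describe Aim 2a as exploratory in a consenting subset. The count is also useful feasibility information for the larger trial.

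Cost: an IRB amendment, a consent line and one extra reported count. No visit or procedure is added. The downside is that some participants will decline the assay line too, so part of the loss will remain.

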4.2 Baseline Visit

The potential participant will return to the urology clinic to review pathology results and treatment options within 4 weeks of TURBT. This is a routine post-TURBT follow-up visit (i.e. baseline visit). If the potential participant is deemed eligible for both radical cystectomy and chemoradiation by the treating urologist, the potential participant will then be randomized either to radical cystectomy arm or chemoradiation arm.

Each participant will be assigned a unique subject identifier (subject ID) that has no meaning external to the study database. The participant identifiers will be further masked and password protected, and stored only on a secure server behind a "firewall". Only authorized research study members will have access to these identifiers. A research study file will be kept for each participant accrued. This file will include the participant's consent, the assigned unique subject identifier, and copies of relevant source documents. All participant records will be securely stored in the Urology research offices at the MARC. A data entry system will be prepared in RedCap for the study. Both the subject identifier, sequence number, and the treatment assignment for each patient will be entered into the database together with clinical outcome data collected across visits.

During this visit, the participant will complete a study questionnaire packet, which may include and not limited to demographics, medical history; and study questionnaires *such as* EORTC QLQ C30 and FACT-BI. In the interest of time, the study questionnaire packet may also be completed at participant's home and return to the study team via mail or email (per participant preference). Study team member will strongly encourage participant to complete the study questionnaire at

the time of baseline visit. If the participant completes the questionnaires from home, a study team member may follow-up with the participant over the phone, if the completed questionnaires are not received within a week of the visit. Two tubes (~ 10 mL or 2 teaspoons each) of research blood will also be drawn. Study team member or clinic staff will record participant's height, weight, and vital signs. At the completion of the baseline measurements, each participant will be randomized to either "Radical Cystectomy" or "Chemoradiation" following a process through sequentially numbered, opaque sealed envelopes by an authorized research study member.

